4.11. Software

Modelling to determine the OBD will be conducted [REDACTED]

[REDACTED] All other general data manipulation and statistical analyses will be conducted using SAS[®] Version 9.4 or higher (SAS[®] Institute, Inc., Cary, North Carolina, United States).

4.12. Study Day and Study Start Date

For assessments prior to DTX301 administration, study day will be defined as the assessment/event date minus date of DTX301 infusion (Day 1). For assessments on or after Day 1, study day will be defined as assessment/event date minus date of DTX301 infusion + 1. Study start date is defined as the date the informed consent form (ICF) is signed.

4.13. Subject Identification

Subjects will be identified in data listings by subject identification number which consists of the subject number concatenated with the site number. Data listings will be sorted by subject identification number, visit, and parameter (where applicable).

4.14. **Unscheduled Visits**

Unscheduled visits will not be included in by-visit summaries of data with the exception of worst post-baseline value in the shift from baseline summary of electrocardiogram (ECG) interpretation and summaries of worst post-baseline value for hematology, chemistry, urinalysis and amino-acid and summaries of newly notable laboratory abnormalities in chemistry relating to liver function test results. Moreover, unscheduled visits will be included into individual patient graphs.

4.15. **Analysis Sets**

4.15.1. **Safety Set**

The Safety Set (SS) will include all subjects who receive DTX301. Subjects who receive a partial dose will be summarized or listed according to the nearest candidate dose (see [Table 3-1](#)) based on the actual dose they received. The SS will be used to tabulate and list all of the safety endpoints, efficacy endpoints, and for the purpose of N-CRM modelling.

4.15.2. **MTD Determining Set**

See Section 3.2.8 for details.

5. **Subject Disposition**

5.1. **COVID-19**

[figure not shown]
At the onset of the Coronavirus Disease 2019 (COVID-19) pandemic in Europe and North America, only 2 subjects in cohort 3 were ongoing [REDACTED]. Due to the spacing of visits and number of ongoing subjects, it was decided to collect the impact of COVID-19 on the visits and/or assessments missed using a specific eCRF page and not to change the planned analysis. This data collection method was planned to be applied to patient [REDACTED] and, if applicable, to all patients of cohort 4 as well. All data collected on this page will be listed in a data listing.

Table 5–1 Pandemic Lock-down Restrictions Start/End Dates

| Country (region) | Lock-down Start Date | Lock-down Stop Date |
|-------------------------|-----------------------------|----------------------------|
| UK | 24-Mar-2020 | 15-Jun-2020 |
| | 05-Nov-2020 | 02-Dec-2020 |
| | 04-Jan-2021 | 12-Apr-2021 |
| Spain | 14-Mar-2020 | 11-May-2020 |
| France* | 17-Mar-2020 | 11-May-2020 |
| | 30-Oct-2020 | 14-Dec-2020 |
| Canada | 13-Mar-2020 | 04-May-2020 |

| | | |
|---------------------|-------------|-------------|
| USA (Massachusetts) | 24-Mar-2020 | 25-May-2020 |
| USA (New York) | 20-Mar-2020 | 10-June-20 |

The start and stop dates correspond to the lock-down in each country/region, travel restriction may have been lifted at a later date in some country/regions.

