Symptomatic hyperammonemic events, classified as hyperammonemic crises (HAC) are often triggered by acute stressors, most commonly concurrent infection, but can become a life-threatening event at any age [Lichter-Konecki 2013; Batshaw 2014]. For example, adults with late-onset OTC deficiency have become hyperammonemic after crush injury, following surgery, when on a high-protein diet, during the postpartum period, and when treated with chemotherapy, high-dose corticosteroids, valproate, or haloperidol [Lichter-Konecki 2013; Batshaw 2014]. Consistent with the Urea Cycle Disorders Consortium (UCDC), we have defined hyperammonemic crisis (HAC) in this study as an episode of signs and symptoms associated with hyperammonemia (such as frequent vomiting, nausea, headache, lethargy, irritability, combativeness, and somnolence), with documented elevated ammonia levels (≥ 100 $\mu\text{mol/L}$) and requiring medical intervention [Kent and Holt 2017; Longo and Holt 2017; Diaz 2019].

Successful rescue from an initial hyperammonemic crisis does not eliminate the chronic risk patients have for developing repeat episodes of hyperammonemia, which may present as lethargy, seizures, or coma. Regardless of the age of onset, neuropsychological complications for all individuals with OTC

Protocol: 301OTC01

deficiency typically include developmental delay, learning disabilities, intellectual disability, attention deficit hyperactivity disorder, and executive function deficits.

The current standard of care for OTC deficiency is to limit dietary protein intake and supplement the diet with a high-energy source, such as glucose [Leonard 2001]. If plasma ammonia is not stabilized by dietary restriction alone, ammonia scavengers that promote an alternative pathway of nitrogen removal can be administered [Batshaw 2001; Häberle 2012; Lichter-Konecki 2013; Häberle 2019]. Ammonia scavengers cannot, however, completely prevent individuals from having hyperammonemic crises [Batshaw 2001]. Orthotopic liver transplantation can correct OTC deficiency; however, this is limited by donor availability and is associated with significant risk of morbidity and mortality [Leonard 2004].

Thus, there remains a significant unmet medical need for a treatment that allows for sustained ammonia management and prevention of hyperammonemic crises associated with OTC deficiency.

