4.2 Exclusion Criteria

Subjects who meet any of the following criteria at Screening will be excluded from the study:

1. At Screening or Baseline (Day 0), plasma ammonia level ≥ 100 $\mu\text{mol/L}$ for patients who historically maintain normal ammonia levels; OR plasma ammonia level ≥ 200 $\mu\text{mol/L}$ for patients who historically are not able to fully control ammonia levels with baseline management; OR signs and symptoms of hyperammonemia, with documented elevated ammonia level, during the 4-week period preceding Day 0. If the ammonia level is inconsistent with the subject's clinical status, the ammonia level may be repeated to ensure accurate results.
2. Liver transplant, including hepatocyte cell therapy/transplant.

Protocol: 301OTC01

3. History of liver disease as evidenced by any of the following: portal hypertension, ascites, splenomegaly, esophageal varices, hepatic encephalopathy, or a liver biopsy with evidence of stage 3 fibrosis.
4. Significant hepatic inflammation or cirrhosis as evidenced by imaging or any of the following laboratory abnormalities: alanine aminotransferase (ALT) or aspartate aminotransferase > the upper limit of normal (ULN), total bilirubin > $1.5 \times$ ULN, alkaline phosphatase > $2.5 \times$ ULN.
5. Serum creatinine > 2.0 mg/dL.
6. Evidence of active hepatitis B virus (HBV) or hepatitis C virus (HCV) infection, documented by current use of antiviral therapy for HBV or HCV or by hepatitis B surface antigen (HBsAg) or HCV RNA positivity. **NOTE:** Subjects with a history of HCV infection must have documentation of 2 negative viral assays by polymerase chain reaction (PCR), collected at least 6 months apart, to be considered negative for HCV. Subjects with a history of HCV infection who test positive for HCV RNA at Screening can be rescreened once, after they have been treated and have documentation of at least 2 negative samples collected at least 6 months apart.
7. History of human immunodeficiency virus (HIV) infection AND any of the following: CD4+ cell count < 350 cells/mm³, change in antiretroviral therapy regimen within 6 months prior to Day 0, or plasma viral load > 200 copies/mL, documented on 2 separate occasions, as measured by PCR.
8. Active infection (viral or bacterial).
9. Anti-AAV8 neutralizing antibody titer \geq 1:5.
10. Participation (current or previous) in another gene transfer study.
11. Participation in another investigational medicine study within 3 months of Screening.

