7.2 Subject Replacement

If a subject withdraws from the study after receiving DTX301, the subject will not be replaced. Subjects who withdraw from the study after signing the ICF, but before receiving DTX301, will be replaced and the replacement subject will be sequentially assigned to treatment with a new subject identification number.

8 Study Assessments and Procedures

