8.2.4.1.2 Treatment for Possible Vector-Induced Hepatitis

The investigator, in conjunction with the Ultragenyx Pharmaceutical Inc. medical lead will consider starting oral steroid treatment, per protocol, for possible vector-induced hepatitis when a subject's **ALT is greater than the ULN** and is considered by the investigator to be related to treatment with DTX301. The subject must be assessed as clinically and metabolically stable, and intercurrent illnesses (eg, viral infection) or concomitant medications known to affect transaminases, be excluded.

Repeat liver function testing for confirmation of results should be considered to inform the use of steroid treatment. If repeat testing is deemed necessary, every effort should be made to repeat the testing within 24 hours from receipt of test results indicating elevated ALT.

At any point between scheduled visits, additional, unscheduled assessment for LFTs, plasma ammonia, or any other biomarker to assess subject safety and clinical status may be performed, at the discretion of the investigator.

Changes to baseline treatment (ie, ammonia scavenger medications and protein-restricted diet) cannot occur while the subject is treated with corticosteroids or within a 2-week period of completing a corticosteroid taper.

Based on available evidence, it is expected that vector-induced hepatitis will be self-limiting. Therefore, oral prednisone (or prednisolone) will be used per the American Association for the Study of Liver Disease guidelines, with a slight modification in **Cohorts 1 to 3**:

- Week 1: prednisone 60 mg/day
- Week 2: prednisone 40 mg/day
- Week 3 and Week 4: prednisone 30 mg/day
- Week 5 and thereafter: prednisone will be tapered by 5 mg/week until liver enzymes return to baseline levels. The use of prednisone will be recorded on the appropriate page in the eCRF.

Protocol: 301OTC01

Cohort 4 (Dosing Process Optimization) will utilize an alternative regimen of corticosteroids, aiming at prophylaxis of vector-induced hepatitis. Therefore, oral prednisone (or prednisolone) will be initiated before dosing with DTX301, sustained for 4 weeks, followed by tapering as described below. Prophylactic corticosteroid regimens are in use for gene transfer therapies [Audentes 2017 Clinicaltrials.gov identifier: NCT03223194; Abeona Therapeutics 2016 ClinicalTrials.gov identifier: NCT02716246].

- At least 5 days prior to dosing: prednisone 60 mg/day

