10.5.3.1 Adverse Events

All statistical analyses of safety outcomes will be descriptive. The incidence of AEs and treatment-emergent AEs will be summarized for each dosing cohort by severity and relationship to study product. Serious AEs will be presented for each dosing cohort by relationship to study product. Summary tables will present incidence estimates and individual event rates by system organ class as well as within each system organ class. Subjects experiencing an event more than once with varying severity will be counted only once, applying only the maximum severity observed within each system organ class and preferred term. For incidence of relationship to study product, subjects will be counted only once, in the category of the strongest relationship to study product within each system organ class and preferred term.

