8.3.12. Subgroup analysis

Graphical displays of time-normalized ammonia and percent of normal ureagenesis activity over time will be provided by gender.

9. Safety Analysis

Safety will be assessed based on AEs, serious adverse event (SAEs), complete and targeted physical examination findings, vital sign measurements, ECG results, clinical laboratory evaluations (clinical chemistry, spot ammonia [included under efficacy section], hematology, urinalysis, and coagulation panel), blood for vector genome determination, measurement of neutralizing antibody to AAV8, measurement of AAV8 binding antibodies, and anti-OTC antibodies [the latter three included under efficacy section]. Assessment of any cell-mediated immune responses to AAV8 and OTC are collected prior to amendment 5. All safety analyses will be conducted for the SS.

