9.1. Adverse Events

An AE is defined as any untoward medical occurrence in a subject enrolled into this study (from the time the subject signs the ICF until their exit from the study) regardless of its causal relationship to study drug. A treatment-emergent adverse event (TEAE) is defined as any event not present before exposure to study drug, or any event already present that worsens in intensity (i.e. severity) or frequency after exposure to study drug. Any events which occur after exposure to study drug and before the first visit of the extension study (301OTC02) will also be considered as TEAEs.

AEs will be coded using MedDRA; the dictionary version used for reporting the study will be described in the relevant table and listing footnotes. Severity/toxicity grade will be defined according to the most current version of the National Cancer Institute Common Terminology Criteria for Adverse Events (NCI-CTCAE).

There are four categories of relationship collected on the eCRF: “Unrelated”, “Possible”, “Probable”, or “Definite”. A related AE is an event where the investigator determined that the relationship to study drug was “Possible”, “Probable”, or “Definite”. For summaries by relationship, AEs with a missing relationship will be considered to be “Possible”. TEAEs will be summarized by strongest relationship. The investigator will also indicate whether

the AE is related to [1-¹³C] sodium acetate, OTC deficiency, hyperammonemia, and as of protocol amendment 5, to corticosteroid regimen.

An HAC-related TEAE is defined as a TEAE which has been identified as associated with the crisis in the eCRF “Hyperammonemic Crisis” page.

If AE start date is missing, it will be imputed as described in the [Appendices](#).

The incidence and the number and percentage of subjects will be summarized by DTX301 dose/prophylactic corticosteroids and overall for each of the following:

- All TEAEs
- All serious TEAEs
- All TEAEs with grade ≥ 3
- All study drug related TEAEs
- All study drug related serious TEAEs
- All study drug related TEAEs \geq grade 3
- All TEAEs related to corticosteroid regimen (prednisone/prednisolone)
- All HAC-related TEAEs
- TEAEs leading to study discontinuation
- Any AE leading to death

The number and percentage of subjects with TEAEs will be summarized by DTX301 dose/prophylactic corticosteroids, overall, SOC, and PT for each of the following:

- TEAEs (including incidence)
- TEAEs by relationship (including incidence)

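### SAP 9.1 omits the all-AE and all-SAE tables in the primary endpoint, so new AEs on Cohort 4's pre-dose prednisone are listed but not tabulated, and subjects never dosed have no AE output

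*SAP*

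**What the plan says.** **The endpoint.** Protocol Section 2, repeated in SAP Table 2-1, makes the incidence of AEs, TEAEs and SAEs by dosing cohort the primary endpoint. Protocol 10.5.3.1 says: "The incidence of AEs and treatment-emergent AEs will be summarized for each dosing cohort by severity and relationship to study product". It adds that serious AEs are presented by cohort and that summary tables give incidence.

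**The analysis set and window.** SAP 4.15.1: "The Safety Set (SS) will include all subjects who receive DTX301". SAP Section 9: "All safety analyses will be conducted for the SS". SAP 9.1: "A treatment-emergent adverse event (TEAE) is defined as any event not present before exposure to study drug", or one already present that worsens afterwards.

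**The outputs.** Every summary in SAP 9.1 is of TEAEs or a subset of them, or of DLTs, with one exception: AEs leading to death. The corticosteroid-related, HAC-related and serious summaries are all of TEAEs. The listings are wider: all AEs, all SAEs, AEs leading to discontinuation and AEs related to the corticosteroid regimen. They too are restricted to the Safety Set.

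**The Cohort 4 regimen.** SAP 3.1 calls the prophylactic steroid regimen the focus of Cohort 4. Protocol 8.2.4.1.2 begins it as follows: "At least 5 days prior to dosing: prednisone 60 mg/day". AEs are collected from consent (protocol 9.1), and their relationship to the corticosteroid regimen is recorded (protocol 9.1.4).

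**The concern.** The tables do not deliver the primary endpoint as written. For most drugs the gap between all AEs and TEAEs is background noise from screening. In Cohort 4 it is not, because part of the regimen under study is given inside that gap.

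The selection may also be informative. The protocol's Introduction says adults with late-onset disease have become hyperammonemic "when treated with chemotherapy, high-dose corticosteroids, valproate, or haloperidol". Exclusion criterion 1 removes a subject with "signs and symptoms of hyperammonemia, with documented elevated ammonia level, during the 4-week period preceding Day 0". Protocol 3.2.2.2 makes dosing conditional on Day 1 ammonia and clinical stability. Protocol 7.2 adds: "Subjects who withdraw from the study after signing the ICF, but before receiving DTX301, will be replaced". A subject who reacted badly to prednisone before dosing could therefore leave before entering the only population for which AEs are reported. What is at stake is whether a reader of the safety tables can see how the regimen was tolerated from its first dose.

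**Working it through.** No stated figure depends on this point, so there is none to reproduce. The check sets the texts side by side and then sizes the window.

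**1. Endpoint against outputs.**

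| Element, by cohort | Primary endpoint | SAP 9.1 table | SAP 9.1 listing (Safety Set) |
|---|---|---|---|
| All AEs | yes | none, except AEs leading to death | yes |
| TEAEs | yes | yes | yes, within all AEs |
| All SAEs | yes | serious TEAEs only | yes |

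SAP Section 12 lists changes from the protocol. The move from AEs to TEAEs is not among them.

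**2. Where an AE on pre-dose prednisone goes.**

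- *Subject later dosed, event new and not worsening after dosing:* not a TEAE, so absent from the SAP 9.1 tables (unless fatal). Present in the all-AE listing and, where it applies, the SAE and corticosteroid-related listings. A hospitalization for hyperammonemic crisis in this window is an SAE (protocol 9.1.1.2) but enters no SAE table.
- *Subject later dosed, event worsening after dosing:* a TEAE, so tabulated.
- *Subject never dosed:* outside the Safety Set, so in no AE table and no AE listing. Disposition (SAP 5.2) covers enrolled subjects, defined by consent and the screening criteria, and the eligibility listing (SAP 6.5) includes those who failed a criterion. Either might show the subject. Neither reports the AE.

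**3. Size of the pre-dose window.** Inputs from protocol 8.2.4.1.2, in calendar days: at least 5 before dosing; 4 weeks × 7 = 28 from Day 1; taper 6 steps × 5 = 30.

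- Total: 5 + 28 + 30 = 63 days. Pre-dose share: 5/63 = 7.9%.
- Days at 60 mg/day: 5 + 28 = 33. Pre-dose share: 5/33 = 15.2%.
- The taper is also labelled Week 5 through Week 8, which is 28 days, not 30. The two need reconciling, but the share barely moves: 5/61 = 8.2%.

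Because 5 days is a minimum, these shares are minima. They measure regimen time, not an effect on any result.

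**4. What a Cohort 4 table can say.** SAP 3.1 closes Cohort 4 after 2 subjects enrolled. If both were dosed and neither had an event, the one-sided 95% upper limit for the event rate is 1 − 0.05^(1/2) = 77.6%. Individual data therefore carry more than any rate, so for Cohort 4 the population covered by the listing matters more than the extra table.

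**The case against.** The strongest reply is that little is hidden. For dosed subjects every pre-dose event is in the listings, and with 2 subjects a listing holds all that a table would. This is right. A reader might infer that pre-dose harm from the steroid regimen is lost; for dosed subjects the documents do not support that.

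Second, the DTX301-based safety population and the TEAE anchor come from the protocol (10.5.3 and 9.1.1.1), and the primary objective is the safety of DTX301, not of prednisone. This also stands. It rules out the reading that the SAP chose a wrong safety set, or that the primary objective rests only on subjects who tolerated the prednisone lead-in.

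Third, the SAP revision history for Version 3.0 describes a pre-dose versus post-dose summary of hyperammonemic crises, with pre-dose meaning the 12 months before dosing. The text of SAP 8.3.2 available to me breaks off after the definition, so this cannot be confirmed or excluded. It could tabulate a pre-dose crisis in a dosed subject. As described it would not isolate the prednisone days, and it has no reference date for a subject never dosed.

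Fourth, a temporarily unstable subject may be rescreened and dosed later (protocol 3.2.1), and no document says that anyone started prednisone and went undosed. It is tempting to set 1 event in 3 steroid-exposed subjects against 0 in 2 reported, but that third subject is hypothetical.

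Finally, protocol 10.5.3.1 says serious AEs are presented, which a listing might satisfy. The primary endpoint, however, is their incidence by cohort.

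What survives is the unrecorded gap between the endpoint and the tables, which affects all cohorts, and the absence of any AE output for steroid-exposed, undosed subjects.

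**Conclusion.** Wrong as written on one count, with a cheap improvement on another.

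- *Wrong as written:* the SAP 9.1 tables do not provide the all-AE and all-SAE incidence by cohort named in the primary endpoint, and Section 12 does not say so. This rests on the text alone.
- *Improvement:* no AE table or listing covers a subject who takes prophylactic prednisone and is never dosed. The group may be empty. If it is not, it is selected partly by a harm that the protocol itself links to high-dose steroids.

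The window concerned is at least 5 of 63 regimen days (7.9%), or 5 of the 33 days at 60 mg/day (15.2%). No numerical effect on a result can be given, because the documents do not say how many subjects started prednisone without being dosed. SAP 3.1 judges the data on the prophylactic regimen sufficient without saying which data were used, so a reader should not infer that this judgement was biased.

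**What to change.** Keep the Safety Set and TEAE definitions, and make these additions:

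1. In SAP 9.1, add all-AE and all-SAE tables by cohort, as the endpoint requires.
2. Add a Cohort 4 table of AEs with onset from the first prophylactic prednisone dose to the DTX301 infusion.
3. Add an AE/SAE listing for everyone who took at least one prophylactic dose, dosed with DTX301 or not, and state how many were never dosed, even if zero.
4. Record these additions in SAP Section 12.

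The cost is SAP wording and a few outputs. AEs and their relationship to the steroid regimen are already collected from consent, so no new data and no change in clinical management are needed. The drawback is a longer at-risk period in Cohort 4 than in Cohorts 1 to 3 for steroid-related events. Showing pre-DTX301 and post-DTX301 onset separately keeps the cohorts comparable.

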5.2. Disposition

Disposition will be summarized for all enrolled subjects (i.e. all subjects who signed the study informed consent and met all Screening Inclusion Criteria and did not meet any Screening Exclusion Criteria) by DTX301 dose/prophylactic corticosteroids and overall. The number and percentage of subjects who have been treated (i.e. SS), have completed the study, are ongoing or discontinued from the study, as well as the primary reason for study discontinuation (if applicable) will be tabulated.

All disposition related information for enrolled subjects will be presented in a data listing.

